6.4. Examples of participant feedback

Below are some examples of the types of feedback that are being considered:

- (a) Questionnaire insights are under development and may include comparisons to healthy recommendations, comparisons to the population, as well as resources participants may wish to consult.
- (b) Baseline physical measurements (blood pressure, height, weight, waist circumference) as well as baseline blood measures of cholesterol. These measurements are not intended to be a 'health check' and are not, for now, shared with their GP or the NHS. However, we are working with the NHS and the Office for Health Improvement and Disparities to explore potential options for sharing these data with the NHS in the future. We will provide written feedback to participants about their blood pressure, heart rate, and cholesterol (from a POCT/ 'finger-prick' test) on a proforma with advice to contact NHS 111, a Pharmacist or GP in the rare circumstances where that is necessary or if they have e(i.e measurements that warrant medical attention immediately or within days e.g. a very low heart rate). For the vast majority of results, we will also direct participants to the NHS website on blood pressure, and the British Heart Foundation website on cholesterol where they can obtain further information and advice.
- (c) Being approached by NHSBT if their genotypes suggest that they have less common minor blood group antigens that are underrepresented among NHSBT blood donors. This may be particularly beneficial for minority groups for whom NHSBT sometimes has difficulty providing optimally matched blood products.
- (d) Providing participants with increased access to information stored in their NHS health care records.
- (e) Integrated risk scores that provide disease risk estimates. Leading integrated risk score candidates that may initially be feedback to participants include cardiovascular disease,⁶² age-related macular degeneration, glaucoma, and type II diabetes. Each of these integrated risk scores provides good risk prediction and are clinically actionable.
- (f) Other examples include risk predictions based on common genetic variants associated with risk of iron overload, deep venous thrombosis, or that influence the efficacy or side effects of prescription drugs.

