If you are currently taking the pill, select 'Still taking the pill'. If you are unsure, please provide an estimate or select 'Do not know'.

[FH6 (UKB)]

Have you **ever** used hormone replacement therapy (HRT)?

SELECT one of 4 from

1 Yes

0 No -> **GO TO FH9**

-1 Do not know -> **GO TO FH9**

-3 Prefer not to answer -> **GO TO FH9**

[FH6A (UKB)]

How old were you when you first used HRT?

Enter INTEGER

[Require \geq 16, \leq current age]

OR

-1 Do not know

OR

-3 Prefer not to answer

If you are unsure, please provide an estimate or select 'Do not know'.

[FH6B (UKB)]

How old were you when you last used HRT?

Enter INTEGER

[Require \geq FH6A, \leq current age]

OR

-1 Do not know

OR

-11 Still taking HRT

OR

-3 Prefer not to answer

If you are currently using HRT, select 'Still taking HRT'.

If you are unsure, please provide an estimate or select 'Do not know'.

[FH9 (UKB)]

Have you had a hysterectomy (womb removed)?

SELECT one of 4 from

1 Yes

0 No -> GO TO FH10

-5 Not sure -> GO TO FH10

-3 Prefer not to answer -> GO TO FH1

[FH9A (UKB)]

How old were you when you had your hysterectomy?

Enter INTEGER

[Require \geq 0, \leq current age]

OR

-1 Do not know

OR

-3 Prefer not to answer

If you are unsure, please provide an estimate or select 'Do not know'.

[FH10 (UKB)]

Have you had BOTH ovaries removed?

SELECT one of 4 from

1 Yes

0 No -> GO TO L1(UKB)

-5 Not sure -> GO TO L1(UKB)

-3 Prefer not to answer -> GO TO L1(UKB)

Only enter 'Yes' if you have had both ovaries removed

If you are unsure of whether both ovaries have been removed, select 'Do not know'.

[FH10A (UKB)]

How old were you when you had BOTH ovaries removed?

Enter INTEGER

[Require ≥ 0 , \leq current age]

OR

-1 Do not know

OR

-3 Prefer not to answer

[L1 (UKB)]

Have you ever been diagnosed with any of the following by a doctor or other health professional?

Please select all that apply

We will ask more details for any type of disorder that you select here

TOGGLE

[Require ≥ 1 choices]

- 6 Autoimmune disorder -> **GO TO AUTO_A**
- 7 Blood disorders (Anaemia) -> **GO TO BLOOD_A**
- 2 Cancer -> **GO TO CANC_A**
- 3 Complications or difficulties in pregnancy or childbirth -> **SHOW IF FEMALE; GO TO PREG_A**
- 4 Digestive system or liver problems -> **GO TO DIG_A**
- 5 Endocrine, nutritional and metabolic disorders (e.g., diabetes, thyroid disorder, vitamin deficiencies) -> **GO TO EN_A**
- 6 Eye or visual problems -> **GO TO EYE_A**

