- 7 Fractures, breaks, or joint problems -> **GO TO FRAC_A**
- 8 Heart or circulatory disease (e.g. high blood pressure or stroke) -> **GO TO HEART_A**
- 9 Kidney or urinary system disorders -> **GO TO KIDN_A**
- 10 Lung or respiratory problems -> **GO TO LUNG_A**
- 11 Mental health conditions (e.g. depression, bipolar disorder) -> **GO TO MH_A**
- 12 Neurodevelopmental conditions (e.g., Autism spectrum disorder, ADHD) -> **GO TO ND_A**
- 13 Neurological disorders (things that affect that brain or nervous system) -> **GO TO NEU_A**
- 14 Reproductive system problems -> **GO TO REPRO_A**
- 15 Other not listed -> **GO TO L5DF**
- 16 None of these -> **GO TO L5DF**
- 1 I don't know **[EXCLUSIVE]** -> **GO TO L5DF**
- 3 Prefer not to answer **[EXCLUSIVE]** -> **GO TO L5DF**

If the diagnosis was for cancer, please select cancer. We will ask more about the type of cancer in a subsequent question.

[AUTO_A]

Have you ever been diagnosed with any of the following autoimmune disorders by a doctor or other health professional?

- 0 Rheumatoid arthritis
- 1 Lupus
- 2 Inflammatory Bowel Disease (IBD)
- 3 Multiple Sclerosis (MS)
- 4 Graves' disease
- 5 Guillain-Barre syndrome
- 6 Psoriasis
- 7 Other (not listed)
- 1 I don't know
- 3 Prefer not to answer

[BLOOD_A]

Have you ever been diagnosed with any of the following types of anaemia by a doctor or other health professional?

- 0 Iron deficiency anaemia
- 1 Vitamin deficiency anaemia
- 2 Sickle cell anaemia
- 3 Aplastic anaemia
- 4 Thalassemia
- 5 Other (not listed)
- 1 I don't know
- 3 Prefer not to answer

[CANC_A (CONNECT)]

Which type(s) of cancer specifically were you diagnosed with?

Please indicate where the cancer originated, even if it spread to other body areas

- 0 Anal
- 1 Bladder
- 2 Brain
- 3 Breast
- 4 Cervical
- 5 Colon/rectal
- 6 Oesophageal

- 7 Head and neck (Including cancers of the mouth, sinuses, nose, or throat. Not including brain or skin cancers.)
- 8 Gastric
- 9 Kidney
- 10 Leukaemia (blood and bone marrow)
- 11 Liver
- 12 Lung or bronchial
- 14 Lymphoma
- 15 Ovarian
- 16 Pancreatic
- 17 Prostate
- 18 Skin
- 19 Stomach
- 20 Testicular
- 21 Thyroid
- 22 Uterine (endometrial)
- 23 Another type of cancer
- 24 I know I had cancer, but don't know what type
- 1 I don't know
- 3 Prefer not to answer

[CANC_B (CONNECT)]

What type of skin cancer specifically were you diagnosed with?

- 9 Melanoma
- 10 Basal cell
- 11 Squamous cell
- 1 I don't know
- 3 Prefer not to answer

[PREG_A (CONNECT+ICD)]

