- 55 Schizophrenia
- 56 Schizoaffective disorder
- 57 Personality disorder
- 58 Other (not listed)
- 59 None of the above
- 1 I don't know
- 3 Prefer not to answer

[ANX_B]

Which anxiety disorder(s) specifically have you been diagnosed with in your lifetime?

- 24 Generalised anxiety disorder
- 25 Agoraphobia
- 26 Social anxiety disorder
- 27 Panic disorder
- 28 Panic attacks
- 29 Specific phobia
- 30 Other (not listed)
- 31 None of the above
- 1 I don't know
- 3 Prefer not to answer

[DEP_B]

Which depressive disorder(s) specifically have you been diagnosed with in your lifetime?

- 15 Major Depressive Disorder
- 16 Perinatal depression
- 17 Postnatal depression
- 18 Other (not listed)
- 19 None of the above
- 1 I don't know
- 3 Prefer not to answer

[EATD_B]

Which eating disorder(s) specifically have you been diagnosed with in your lifetime?

- 18 Anorexia nervosa
- 19 Atypical anorexia nervosa
- 20 Bulimia nervosa
- 21 Binge eating disorder
- 22 Other (not listed)
- 23 None of the above
- 1 I don't know
- 3 Prefer not to answer

[NEU_A]

Have you ever been diagnosed with any of the following neurological or brain disorders by a doctor or other health professional?

- 24 Epilepsy
- 25 Parkinson's disease
- 26 Alzheimer's disease/dementia
- 27 Early onset Alzheimer's disease/dementia
- 28 Vascular dementia
- 29 Migraine with aura
- 30 Migraine without aura
- 31 Other (not listed)
- 1 I don't know
- 3 Prefer not to answer

[REPRO_A (CONNECT)]

Have you ever been diagnosed with any of the following conditions by a doctor or other health professional?

- 0 Endometriosis [validation show if question refers to female]

- 1 Polycystic Ovary Syndrome (PCOS) [validation show if question refers to female]
- 2 Enlarged prostate [validation show if question refers to male]
- 3 Fibrocystic Breast, or another Benign Breast Disease (such as proliferative Benign Breast Disease or LCIS)
- 4 Ductal Carcinoma in situ (DCIS)
- 5 Uterine Fibroids
- 6 Other (not listed)
- 1 I don't know
- 3 Prefer not to answer

[L5DF]

DO YOU REGULARLY TAKE ANY OF THE FOLLOWING TYPES OF MEDICATIONS? (YOU CAN SELECT MORE THAN ONE ANSWER)

- 0 Medication for autoimmune disorders > GO TO
AUTO_MEDS_A
- 1 Medication for bone health -> GO TO
BONE_MED_A
- 2 Treatment for Cancer -> GO TO
CANC_MED_A
- 3 Medication for diabetes or diabetic health -> GO TO DIA_MED_A
- 4 Medications for Digestive problems (including acid reflux and liver problems)-
> GO TO DIG_MED_A

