- 5 Medications for Endocrine disorder (e.g., under or over-active thyroid) ->
GO TO ENDO_MED_A
- 6 Medications for heart or circulatory health (e.g., high blood pressure or
stroke) -> **GO TO HEART_MED_A**
- 7 Medication for lung or breathing problems (including asthma) -> **GO TO**
LUNG_MED_A
- 8 Medication for mental health conditions and insomnia (e.g., Depression,
bipolar disorder) -> **GO TO MH_MED_A**
- 9 Medication for neurological disorders (e.g., Alzheimer's, epilepsy,
Parkinson's)-> **GO TO NEURO_MED_A**
- 10 Pain relief medication -> **GO TO PAIN_MED_A**
- 11 Medication for reproductive or sexual health (including contraception,
erectile dysfunction, menopause or hormone medication) -> **GO TO**
REPRO_MED_A
- 12 Supplements, vitamins, or nutritional health -> **GO TO SUPP_MED_A**
- 13 Herbal remedies -> **GO TO HERBAL_MED_A**
- 14 I take medication but I don't know what they're for -> **GO TO**
OTHER_MEDS_A
- 15 None of these -> **GO TO PHQ_TRIG**

- 1 I don't know [EXCLUSIVE] -> GO TO PHQ_TRIG
- 3 Prefer not to answer [EXCLUSIVE] -> GO TO PHQ_TRIG

By regularly we mean something you take on a fixed schedule, or on most days of the week for the last four weeks. Please also tell us about implants or slow release injections that you have or regularly receive

[AUTO_MED_A]

Do you regularly take any of the following medication? (You can select more than one answer)

- 0 Amino salicylates (5-ASAs, mesalazine)
- 1 Azathioprine
- 2 Corticosteroids (e.g., prednisolone)
- 3 Disease-modifying anti-rheumatic drugs (DMARDs, e.g., methotrexate, leflunomide, hydroxychloroquine, sulfasalazine)
- 4 Tacrolimus
- 5 JAK inhibitors
- 6 Tumour Necrosis Factor (TNF) inhibitors
- 7 Tocilizumab
- 8 Rituximab
- 9 Mycophenolate
- 10 Cyclosporine
- 11 Other not listed
- 1 I don't know
- 3 Prefer not to answer

By regularly we mean something you take on a fixed schedule, or on most days of the week for the last four weeks.

If you know you take a medication regularly, but don't recognise these names, please check the packaging. Sometimes the brand names on the packaging will not be the same as the key ingredients.

[BONE_MED_A]

Do you regularly take any of the following medication? (You can select more than one answer)

- 0 Bisphosphonates (e.g., alendronic acid, ibandronic acid, risendronic acid, zoledronic acid)
- 1 Selective oestrogen receptor modulators (SERMs, Raloxifene)
- 2 Strontium Ranelate
- 3 Monoclonal antibodies (Denosumab, Romosozumab)

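### The medication gate L5DF has no answer for other medication, so a participant whose only regular medicine is of an unlisted type gets the same code as one taking nothing, and the follow-up item named for code 14 does not exist

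*Protocol*

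**What the plan says.** Item L5DF (Protocol, Appendix E, Section 5, Your health history) is a multi-select gate: "DO YOU REGULARLY TAKE ANY OF THE FOLLOWING TYPES OF MEDICATIONS". Codes 0 to 13 name fourteen types: autoimmune, bone, cancer, diabetes, digestive, endocrine, heart and circulation, lung, mental health and insomnia, neurological, pain, reproductive and sexual health, supplements, and herbal remedies. The last of these is "Herbal remedies -> GO TO HERBAL_MED_A".

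Code 14 follows, "I take medication but I don't know what they're for", which is routed to OTHER_MEDS_A. Then comes "15 None of these -> GO TO PHQ_TRIG". The only remaining answers are don't know (-1) and prefer not to answer (-3). Those two are tagged exclusive; code 15 is not.

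The diagnosis gate L1, a few pages earlier in the same section, is built differently. It has a category "Eye or visual problems" and one for kidney or urinary disorders. It also gives "Other not listed -> GO TO L5DF" as code 15, separate from a none-of-these answer at code 16.

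**The concern.** A gate question should let the analyst tell three groups apart: those on a listed type, those on something else, and those on nothing. L5DF has no place for the second group. Its members either merge with the third group or, if they also take a listed type, lose the unlisted medicine from the record.

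The protocol relies on this questionnaire for medication data. Section 3.6 lists medications among the topics of a questionnaire meant for what linkage cannot easily supply, and section 2.4 gives over-the-counter medicines as an example of what medical records miss. Section 3.7 says the short questionnaire will be drawn from the same items, so the fault would carry over if L5DF is retained there.

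**Working it through.** No plan figure is involved, so the check is to follow the routing and compare the two gates.

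1. **Answers available in L5DF.** Fourteen named types (codes 0 to 13), plus code 14, code 15, -1 and -3, make 14 + 1 + 1 + 2 = 18 answers. None of them means another kind of medication, and none names eye or kidney/urinary medicines.

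2. **Participant A: glaucoma drops only, purpose known.** Codes 0 to 13 do not apply. Code 14 is untrue, because A knows what the drops are for. A is neither unsure (-1) nor declining (-3). Code 15 is the only accurate answer, and it leads to PHQ_TRIG.

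3. **Participant B: no regular medicine.** Code 15 again, with the same route to PHQ_TRIG. A and B have identical L5DF data and see no medication list. If *a* people take nothing and *b* take only unlisted medicines, code 15 holds *a* + *b* people, and the misclassified share is *b*/(*a* + *b*). The protocol gives neither number.

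4. **Participant C: a statin and glaucoma drops.** C ticks the heart type and is not in code 15, but nothing captures the drops. Every list opened by L5DF except the one for cancer treatment has an "Other not listed" answer, but each is reached only by ticking its own type.

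5. **Participant D: takes a medicine without knowing its purpose.** Code 14 sends D to OTHER_MEDS_A. The last medication item in Appendix E is HERBAL_MED_A, and PHQ_TRIG follows it directly. Other labels differ slightly from their targets (AUTO_MEDS_A and AUTO_MED_A, SUPP_MED_A and SUPPL_MED_A), but in those cases the intended item is obvious. OTHER_MEDS_A has no counterpart.

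6. **L1 beside L5DF.**

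| Answer | L1 (diagnoses) | L5DF (medication) |
|---|---|---|
| Eye | yes | no |
| Kidney/urinary | yes | no |
| Other, not listed | yes, code 15 | no |
| None of these | yes, code 16 | yes, code 15 |

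The questionnaire can therefore record that A has glaucoma (EYE_A lists it) but not that A is treated for it.

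**The case against.** The case for leaving L5DF alone has several parts.

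- **The answer is literally correct.** The stem asks about the listed types, so code 15 means none of those types. This stands, and the protocol nowhere defines code 15 as unmedicated or says researchers will use it that way. But the questionnaire then has no answer that identifies people on no regular medicine.
- **Linkage fills the gap.** Agreeing to linkage is a condition of joining (section 5), and primary care data include prescribing and dispensing (section 5.1). This stands for prescribed medicines. It does not cover over-the-counter products. Many of those are asked about elsewhere (pain relief, indigestion remedies, laxatives, supplements, herbals), so the remaining loss is confined to unlisted types.
- **The diagnosis items separate the groups.** They do so in part. A glaucoma diagnosis with code 15 flags someone who may be treated, but does not show that they are.
- **Some apparent gaps are not gaps.** This stands. Enlarged prostate sits under reproductive problems in REPRO_A, so its treatment fits option 11 of L5DF. L1 has no skin category either, although its 'other' answer would catch skin conditions. Iron, folate and vitamin B are in the supplement list, and anticoagulants are in the heart list. The mismatch of categories therefore holds only for eye and kidney/urinary.

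A reader might also infer a large number from Appendix A. At 5 million participants, dermatitis (116,500), benign prostatic hyperplasia (48,225), urinary incontinence (38,900) and glaucoma (18,200) sum to 221,825. That total cannot be used here. Those are new diagnoses in the 2.5 years of follow-up, whereas L5DF is answered at baseline. The total also counts diagnoses, not people, includes the prostate condition that option 11 covers, and says nothing about who is treated or takes no listed medicine.

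Nor does glaucoma's place among the leading risk-score candidates in section 6.4 ("age-related macular degeneration, glaucoma, and type II diabetes") raise the stakes, because nothing there says that a score uses L5DF.

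**Conclusion.** The point holds as a misclassification fault in one baseline variable and a routing error in one answer. Followed as written, L5DF gives a single code to people taking no regular medicine and to people whose only regular medicine is of a known but unlisted type. It drops the unlisted medicine of people who also take a listed one, and it sends code 14 to an item that is not in Appendix E.

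The size is unknown. It depends on how many participants at baseline take only unlisted medicines, which the documents do not give. The claim that the groups can never be separated would go too far, since linked prescriptions and the diagnosis items recover part of the loss. What the questionnaire alone cannot do is identify the unmedicated, or record over-the-counter medicines of unlisted types. The conclusion assumes that participants answer accurately and that the routing is built as printed. It is a modest fault, worth correcting because the repair is small and unrecorded answers cannot be recovered in full later.

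**What to change.** In L5DF:

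- Add 'Other medication not listed above' before code 15.
- Reword code 15 as 'I do not regularly take any of these or any other medication', and tag it exclusive.
- Write the missing follow-up item (free text or a look-up list) in place of OTHER_MEDS_A, and route both code 14 and the new answer to it.
- Optionally, add eye and kidney/urinary medication types to match L1.

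The cost is a wording change, one added answer and one defined item. It takes a few seconds for those who select it, plus coding work if free text is used.

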1.1 Governance

[figure not shown]
- 1.1.1 Our Future Health, a company established to govern the Our Future Health research programme, is a company limited by guarantee (Number 12212468), incorporated in England on 17th September 2019. The registered office address is [name]. The Articles of Association were last amended on 10th December 2019. Our Future Health is also registered as a charity registered with the Charity Commission for England and Wales (Charity Number 1189681) and OSCR, Scottish Charity Regulator (Charity Number SC050917).
- 1.1.2 Our Future Health Trading Limited is a private limited company (Number 12599493) which is wholly owned by Our Future Health. It was incorporated in England on 13th May 2020 and has the same registered office as Our Future Health. The Articles of Association have not been amended since incorporation. The relationship between Our Future Health and Our Future Health Trading Limited is set out in an Intercompany Agreement. Details of the current trustees and directors of both entities can be found in Appendix A.
- 1.1.3 The Our Future Health research programme is solely governed by Our Future Health.

1.2 Our Board of Trustees

- 1.2.1 The Board of Trustees of Our Future Health (“Board”) is responsible for the governance and strategy of Our Future Health. The Board currently comprises of 4 trustees, comprising a mix of medical and scientific expertise. The trustees have full legal responsibility for the actions of Our Future Health. The trustees are appointed for a renewable term of 3 years and are the directors of the company for the purposes of the Companies Act 2006. Details of the current trustees and directors can be found in Appendix A.
- 1.2.2 The Board meets at least four times a year. They delegate day to day responsibility for the running of Our Future Health to the Executive Team. The Executive Team of Our Future Health and Our Future Health Trading Limited consists of the Chief Executive Officer and their direct reports, all of whom are employees of Our Future Health.
- 1.2.3 The Board has approved and adopted a Conflicts of Interest Policy.

1.3 Our governance structures

1.3.1 The Board also delegates specific responsibilities either directly to a sub-committee of the Board – for example, Audit & Risk – or to the Executive Team which has overall responsibility day to day for the delivery of the Our Future Health research programme and shall manage all operations and logistics of establishing and making the Resource available to researchers. The “Resource” (when used in this document) means the data and samples which will be provided via the Our Future Health research programme along with access to the same via related tools including the Our Future Health Trusted Research Environment. The governance committees are delegated certain tasks required of the Board and these committees are accountable for them. For the Executive Team to operate effectively, they have established operational and advisory boards to support them in delivering the research programme. The operational boards work with the Executive Team to review and make recommendations to the Board on operational matters, while the advisory boards provide additional external expertise into strategic and operational aspects of the research programme either directly via the Executive Team and/or via the operational boards.

In addition to the boards noted above, Our Future Health will shortly establish, in consultation with the Founders Board, a Data Privacy & Information Security Committee/Board for the research programme and Resource.

2. **Audit & Risk Committee**

2.1 **Purpose**

2.1.1 The purpose of the Audit and Risk Committee (“Committee”) is to provide formal and transparent arrangements for applying financial reporting internal control principles and to maintain an appropriate relationship with the Charity’s auditors.

2.2 **Constitution and membership**

2.2.1 The Committee has been established as a committee of the Board by resolution of the Board.

2.2.2 The members of the Committee will be appointed by the Board, on the recommendation of the Nomination and Remuneration Committee and in consultation with the chair of the Committee and the following paragraphs will govern the constitution of the Committee:

2.2.2.1 The Committee will comprise at least three members;

2.2.2.2 The Chair of the Charity will not be a member of the Committee;

2.2.2.3 At least one member of the Committee should have recent and relevant financial experience with competence in accounting and/or auditing; and

2.2.2.4 The Committee as a whole must have competence relevant to the health sector.

2.2.3 The chair of the Committee will be appointed by the Board, on the recommendation of the Nomination and Remuneration Committee. In the absence of the Chair of the Committee, the members present will select one of their number present to chair the meeting.

2.2.4 Appointments to the Committee will be for a period of up to three years, which may be extended by no more than two further periods of up to three years, provided the person still meets the criteria for membership of the Committee.

2.2.5 The Governance Manager will act as the secretary of the Committee.

